### Summary of Changes from Previous Version:

| Affected Section(s) | Summary of Revisions Made | Rationale |
|---------------------|---------------------------|-----------|
|                     |                           |           |
|                     |                           |           |

## 1 PROTOCOL SUMMARY

*Leave blank. Text should be included under the relevant subheadings below.*

### 1.1 SYNOPSIS

**Title:** The RELIEF Ureteral Stent vs. Standard DJ Stent – Assessment of Retrograde Urinary Reflux

**Study Description:** Assessment of retrograde urine reflux after placement of the RELIEF® Ureteral Stent using cystography after contrast gravity-filling of the bladder and assigning a urinary reflux grade.

Randomized controlled trial for evaluation of the stent placement and the adequacy of short-term drainage (defined as the presence of the stent in the ureter and the lack of surgical or other intervention to treat symptoms associated with the stent itself on the stented side during the first 48 hours).

**Primary Objective:** Assessment of retrograde urine reflux after placement of a ureteral stent using cystography after contrast gravity-filling of the bladder and assigning a urinary reflux grade based on standard scoring.

**Secondary Objectives:** Assessment of stent symptoms (incidence, relationship to device, severity) attributed to the ureteral stent; Reporting the Ureteral Stent Symptoms Questionnaire (USSQ) before stent placement, after placement at day 3, prior to removal and post removal; Visualization of distal coil floating in bladder (Y/N) after stent placement

**Primary Endpoint:** Study success defined as adequate short-term drainage defined as the presence of the stent in the ureter and the lack of surgical or other intervention to treat symptoms associated with the stent itself on the stented side during the first 48 hours [Day 0-2] following placement.

**Secondary Endpoints:** USSQ Scale (Ureteral Stent Symptoms Questionnaire) [Time Frame: Day 3 as endpoint, Unplanned hospital visits or doctor visits related to the stent, Medication use

**Description of Sites/Facilities Enrolling Participants:** UC San Diego

**Description of Study Intervention:** Randomized Controlled Trial

**Study Duration:** 1 year

**Participant Duration:** 1 year

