## 3 OBJECTIVES AND ENDPOINTS

We hypothesize that the RELIEF stent will offer the same function as a traditional stent with the added benefits of 1) prevention of urinary reflux and 2) reduction of irritative bladder symptoms.

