**Primary Objectives:**

- Assessment of retrograde urine reflux after placement of a ureteral stent using cystography after contrast gravity-filling of the bladder and assigning a urinary reflux grade based on the following standardized scoring system:
  - Grade I: urine refluxes into the ureter only.
  - Grade II: urine refluxes into the ureter and up to the kidney without dilation.
  - Grade III: urine refluxes into the ureter and kidney and causes mild dilation.
  - Grade IV: urine refluxes into ureter and kidney and causes dilation without twisting of the ureter.
  - Grade V: urine refluxes into ureter and kidney and causes significant dilation with twisting of the ureter.

- Evaluation of the stent placement and the adequacy of short-term drainage (defined as the presence of the stent in the ureter and the lack of surgical or other intervention to treat symptoms associated with the stent itself on the stented side during the first 48 hours).

[figure not shown]

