### 9 STATISTICAL CONSIDERATIONS

#### 9.1 STATISTICAL HYPOTHESES

Primary Efficacy Endpoint: presence of reduced ureteral reflux in Relief stent compared to standard ureteral stent.

Comparative statistics will be employed between the two groups. Findings will be reported as the median and interquartile range (IQR) for continuous variables, and percentages and frequencies for categorical variables. To evaluate difference in the incidence of retrograde reflux (primary endpoint: present, absent) and grading between both arms (primary endpoint; Grades I, II, III, IV, V) Chi-square or Fishers exact test will be used as appropriate.

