#### 9.2 SAMPLE SIZE DETERMINATION

At our target enrollment of 50 patients (25 patients in each arm), a power analysis for our primary endpoint (differences in incidence of retrograde urine reflux between randomized study arms) determined that our study will be sufficiently power (80%) to detect a moderate effect size ( $\omega = 0.4$ ) at an alpha level of 0.05.

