### 9.4 STATISTICAL ANALYSES

#### 9.4.1 GENERAL APPROACH

Findings will be reported as the median and interquartile range (IQR) for continuous variables, and percentages and frequencies for categorical variables. To evaluate differences in the incidence of retrograde reflux (Primary endpoint; present, absent) and grading between both arms (Primary endpoint; grades I, II, III, IV, V), chi-square or fishers exact test will be used as appropriate. To analyze USSQ findings between study arms (secondary endpoint), Mann-Whitney U test or independent t-tests will be used for comparisons of continuous variables and chi-square or fishers exact test for comparisons of categorical variables.

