#### 9.4.2 ANALYSIS OF THE PRIMARY EFFICACY ENDPOINT(S)

To evaluate differences in the incidence of retrograde reflux (Primary endpoint; present, absent) and grading between both arms (Primary endpoint; grades I, II, III, IV, V), chi-square or fishers exact test will be used as appropriate.

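### The plan names different primary endpoints in different sections, and nothing ranks reflux incidence against reflux grade

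*Combined protocol and SAP*

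**What the plan says.** The documents give four versions of the primary endpoint.

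- **Section 1.1 (Synopsis).** The primary endpoint is drainage over the first 48 hours and nothing else: "Study success defined as adequate short-term drainage defined as the presence of the stent in the ureter", with no intervention for stent symptoms. The primary objective in the same synopsis is reflux on cystography, "assigning a urinary reflux grade based on standard scoring".
- **Section 3.** Drainage, reflux grade and visualization of the distal coil all stand under the primary effectiveness heading, unranked. Coil visualization is also a secondary objective. The hypothesis is that "the RELIEF stent will offer the same function as a traditional stent", with less reflux and fewer symptoms as added benefits. A separate primary safety endpoint covers symptoms and unplanned visits.
- **Sections 4.2 and 9.2.** The size rests on "a power analysis for our primary endpoint (differences in incidence of retrograde urine reflux between randomized study arms"), with 50 patients, w = 0.4, alpha 0.05 and 80% power.
- **Sections 9.1, 9.4.1 and 9.4.2.** Two endpoints carry the primary label: "incidence of retrograde reflux (Primary endpoint; present, absent) and grading between both arms (Primary endpoint; grades I, II, III, IV, V"). Both are to be tested by chi-square or Fisher's exact test.

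Section 8.1 bears on the ranking. It calls reflux the primary objective and drainage an additional one.

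**The concern.** A reader who follows the text cannot tell which single result decides the trial. Three things depend on it.

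- **Power.** The 80% belongs to reflux incidence. It is not a statement about the synopsis endpoint, and it is not shown for grade.
- **Error control.** Two tests carry the primary label and only one alpha of 0.05 is given. The plan does not say whether either test suffices or both are needed. If they disagree, the choice is made after the data are seen, in an open-label trial (Section 4.1).
- **Drainage.** The synopsis endpoint has no named test, expected rate, margin or power in Section 9, so the equal-function hypothesis in Section 3 has no decision rule.

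Section 10.1.1 also lists meeting the primary endpoint as a ground for stopping. That ground cannot be applied until there is one primary endpoint.

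**Working it through.** **1. Reproduce the stated power.** Inputs from Sections 4.2 and 9.2: N = 50, w = 0.4, alpha = 0.05. A 2×2 table has df = 1, and a 1-df chi-square test is equivalent to a two-sided test (the plan does not state sidedness).

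- Noncentrality = N × w² = 50 × 0.16 = 8.
- Critical value of chi-square, df = 1, at 0.05: 3.841.
- Power = P(noncentral chi-square(1, 8) > 3.841) = **80.7%**. The smallest N giving 80% is 50.

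The plan's figure is right for one test of incidence at the full 0.05. It is an approximate chi-square figure. The documents give no reflux rates; 70% vs 30% is one assumed pair with w = 0.4, since (0.70 − 0.30) / (2 × √(0.5 × 0.5)) = 0.4. For that pair, full enumeration at 25 per arm gives 78.2% power with Fisher's exact test. Other assumed pairs with w = 0.4 (mean reflux rate 30% to 70%) give 74.4% to 78.2%.

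**2. Grade at the same effect size.** Same noncentrality of 8, all 50 patients:

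| Grade test | df | Critical value | Power |
|---|---|---|---|
| Five categories (I to V) | 4 | 9.488 | 60.5% |
| No reflux plus I to V | 5 | 11.070 | 56.4% |

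The scale in Section 3 has no level for absent reflux, so the plan does not fix which row applies. If only patients with reflux are graded, fewer than 50 enter: at the assumed 70% vs 30%, 25 × 0.7 + 25 × 0.3 = 25 patients on average. In the other direction, w rises if the grade mix also differs between arms. With three assumed milder mixes on RELIEF and 70% vs 30% reflux, w is 0.425, 0.482 and 0.571, and the df = 5 power is 62.4%, 75.3% and 89.6%.

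**3. False positives if a win on either test counts.** There is no true difference, 25 per arm, and each test is at 0.05. Reflux rates and grade mixes are assumed. Incidence alone was enumerated exactly at 30% and 50% without reflux; the either-test figures are simulated.

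| Test rule | Incidence alone | Incidence or grade |
|---|---|---|
| Fisher throughout | 2% to 3% | about 6% to 8% |
| Uncorrected chi-square, Fisher if an expected count is below 5 | 5.3% to 6.5% | about 7% to 11% (7.3% to 10.8%) |

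The plan leaves the choice between the tests open, so both rows are needed.

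**4. Cost of keeping both as primary.** A Bonferroni split at 0.025 each lowers incidence power to 72.1% at N = 50; 80% would need N = 60.

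**5. Drainage.** No power can be calculated, because the documents supply no rate, margin or test.

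**The case against.** The best defence is that the intent is plain. The title, the power statements in 4.2 and 9.2, the hypothesis in 9.1 and the ranking in 8.1 all point to reflux, which leaves the synopsis endpoint line as a drafting slip. On drainage versus reflux this largely stands. It does not settle the matter, because 8.1 ranks objectives rather than endpoints, Section 3 still puts drainage under the primary heading, and no passage ranks incidence against grade.

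Four stronger readings are tempting, and the documents do not support them.

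- *That the trial could be declared a success on drainage with reflux null.* The success definition refers to the stented side in the first 48 hours and can be read as a per-patient criterion, not a verdict on the trial. The wording is loose and should be closed off, but it is not a stated decision rule.
- *That 50 patients cannot show equal drainage.* No non-inferiority test is planned and no margin is given. Any such power figure would depend on a margin invented by the reader.
- *That drainage has no analysis at all.* Section 9.1 promises comparative statistics, with percentages and frequencies for categorical variables, and 8.1 says how drainage is ascertained. What is missing is a named test and a criterion.
- *That the false-positive rate simply doubles to about 10%.* That is near the top of the range only. With Fisher throughout it is about 6% to 8%.

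**Conclusion.** The contradiction is explicit and must be resolved before outcomes are compared between arms. It is a fault of consistency and multiplicity, not of arithmetic: 80% power is correct for reflux incidence by the approximate chi-square test.

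The size is moderate. A grade test at w = 0.4 has roughly 56% to 60% power if all 50 patients enter, and more if the grade mix differs between arms. An either-test claim adds a few percentage points of false-positive risk. Those error figures rest on assumed reflux rates and grade mixes, and on a win on either test being enough. If both tests had to succeed, no alpha split would be needed, but power would fall. The textual conflict rests on no assumption.

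**What to change.** - In 1.1, 3, 9.1, 9.4.1 and 9.4.2, name reflux incidence (present or absent on the post-stent cystogram) as the single primary efficacy endpoint, two-sided alpha 0.05, consistent with 4.2, 8.1 and 9.2. Align the primary objectives in 1.1 and 3.
- Make reflux grade secondary, or test it second in a fixed sequence after incidence. State whether patients without reflux enter the grade comparison.
- Make drainage and distal-coil visualization secondary. Report drainage by arm with the difference and a 95% confidence interval, and treat the equal-function hypothesis as descriptive.
- State that study success is a per-patient drainage criterion, not the trial's verdict.
- State that the primary safety endpoint in Section 3 lies outside the efficacy alpha.
- If the sponsor keeps drainage or grade as primary or co-primary, give its hypothesis, test, alpha rule and power.

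The cost is wording. No patients or procedures are added, and N = 50 stands on the sponsor's chi-square calculation. The downside is that drainage can no longer be headlined as the primary result, and grade becomes supportive. The Schedule of Activities (1.3) has no row for the post-stent cystogram; that is an operational gap to raise separately.

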### 1.2 SCHEMA

See section 1.3

### 1.3 SCHEDULE OF ACTIVITIES (SOA)

| Procedures                            | Screening/Enrollment
Day -90 to -1 | Stent Placement
(Day 0)         | Post-Stenting, Visit 1
(Day 1) | Follow up Phone call
(Day 3)  | Stent Removal
(Day 7-10) | 2-days Post Stent
Removal
(Day 9-12) |
|---------------------------------------|---------------------------------------|------------------------------------|-----------------------------------|----------------------------------|-----------------------------|--|
| Informed consent                      | X                                     |                                    |                                   |                                  |                             |  |
| Demographics                          | X                                     |                                    |                                   |                                  |                             |  |
| Medication Review                     | X                                     | X                                  | X                                 | X                                | X                           | X  |
| Randomization                         |                                       | X                                  |                                   |                                  |                             |  |
| Ureteral Stent Symptoms Questionnaire |                                       |                                    | X                                 | X                                | X                           | X  |
| RELIEF Ureteral Stent or DJ Stent     |                                       | X (placement per standard of care) |                                   | X (removal per standard of care) |                             |  |
| Intraoperative Post Stent Photo       |                                       | X                                  |                                   |                                  | X                           |  |
| Adverse event review and evaluation   |                                       | X                                  | X                                 | X                                | X                           | X  |
| Clinical Usability Survey             |                                       | X                                  |                                   |                                  |                             |  |

## 2 INTRODUCTION

### 2.1 STUDY RATIONALE

Traditional ureteral stents are commonly used in practice to relieve renal obstruction or as a scaffold to promote healing after endoscopic or open/ laparoscopic surgeries involving the ureter [1]. However, morbidities can be associated with placing these stents such as pain or irritative bladder symptoms, which are felt in part to be due to urinary reflux up the stent. The RELIEF stent has the potential to improve urinary symptoms due to its unique structural design, which allows the ureteral orifice to close naturally and reduce the reflux of urine back into the kidney. This study seeks to assess whether the RELIEF stent has less reflux and, therefore, less irritative symptoms.

### 2.2 BACKGROUND

The most commonly reported symptoms include urgency, urinary frequency, dysuria, incontinence, hematuria, suprapubic discomfort, fever due to urinary tract infections and flank pain and they can occur in up to 80% of stented patients. Sometimes, the symptoms are poorly tolerated and can negatively affect the patient's quality of life [2, 3].

Shao et al have studied the relationship between bladder filling and the renal pelvic pressure (RPP) in stented patients, which revealed that RPP increases mildly during bladder filling and dramatically during voiding, indicating the occurrence of urinary reflux. As a result, the authors encouraged early removal of the stents [4]. Another study showed that patients with stents whose distal coils cross the midline are at higher risk of post-stenting morbidities [5].

### 2.3 RISK/BENEFIT ASSESSMENT

### 2.3.1 KNOWN POTENTIAL RISKS

There is a potential risk of loss of confidentiality of data. Every effort will be made to keep the patients' information confidential.

The study participants may feel uncomfortable while addressing some of the questions in the pain questionnaire. They may refuse to answer any of these questions. They may stop their participation in this study at any time.

The standard of care surgical risks and risks with either of the stents should have been reviewed with their surgeon.

Patients who participate in this research study will not get to select the type of stent they will receive.

The principal investigator for this research project has determined and verified that all imaging scans prescribed for this project would typically be performed as part of the standard medical care required to adequately monitor the participant's current illness. If they are especially concerned with radiation exposure, or they have had a lot of x-rays or imaging scans already, they should discuss this with the principal investigator for this project, [name], or their regular doctor.

### 2.3.2 KNOWN POTENTIAL BENEFITS

There is potential direct benefit for the patients assigned to the RELIEF stent group as we suspect it will provide relief from discomfort during recovery after ureteroscopy. The knowledge to be gained from this research is whether the Relief stent reduces urinary reflux and decreases postoperative pain and discomfort for patients who undergo kidney stone surgery and stent placement. If the Relief stent provides improvement in symptoms, this will improve patient care and comfort.

### 2.3.3 ASSESSMENT OF POTENTIAL RISKS AND BENEFITS

The group of investigators, including the principal investigator, and the research support staff will monitor for adverse events. Data will be reviewed quarterly to ensure it is accurate, complete, and its collection complies with the protocol. There will also be a continual assessment of the risks and benefits.

[figure not shown]
Furthermore, Case report forms will be generated for each subject and completed by the investigator or study coordinator. The investigator or study coordinator will countersign each form. After the case report forms for a visit are completed, the research coordinator will enter a limited set of data into a Redcap data management system. Original case report forms will be securely maintained at the clinical sites. Completed copies of the case report forms will be sent to the research coordinator where they will be stored on a secure hard drive. Subjects will be asked to report any adverse events to the study coordinator or physician. All adverse events will be reported on a standardized form that will elicit the number and specify the type of tests used, therapy (or therapies) used, and clinical visits (office, ER and hospitalization) required until the event is resolved.

## 3 OBJECTIVES AND ENDPOINTS

We hypothesize that the RELIEF stent will offer the same function as a traditional stent with the added benefits of 1) prevention of urinary reflux and 2) reduction of irritative bladder symptoms.

**Primary Objectives:**

- Assessment of retrograde urine reflux after placement of a ureteral stent using cystography after contrast gravity-filling of the bladder and assigning a urinary reflux grade based on the following standardized scoring system:
  - Grade I: urine refluxes into the ureter only.
  - Grade II: urine refluxes into the ureter and up to the kidney without dilation.
  - Grade III: urine refluxes into the ureter and kidney and causes mild dilation.
  - Grade IV: urine refluxes into ureter and kidney and causes dilation without twisting of the ureter.
  - Grade V: urine refluxes into ureter and kidney and causes significant dilation with twisting of the ureter.

- Evaluation of the stent placement and the adequacy of short-term drainage (defined as the presence of the stent in the ureter and the lack of surgical or other intervention to treat symptoms associated with the stent itself on the stented side during the first 48 hours).

[figure not shown]
**Secondary Objectives:**

- Assessment of pain or irritative symptoms attributed to the ureteral stent as well as unplanned return visits to ED, OR, or clinic.
- Reporting the Ureteral Stent Symptoms Questionnaire (USSQ) before stent placement, after placement at day 3, prior to removal and post removal.
- Visualization of distal coil floating in bladder (Y/N), after stent placement.

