**Study Endpoints:****1- Primary effectiveness endpoint:**

- Study success defined as adequate short-term drainage defined as the presence of the stent in the ureter and the lack of surgical or other intervention to treat symptoms associated with the stent itself on the stented side during the first 48 hours [Day 0-2] following placement.
- [Note: In some cases, the ureteral stent may not be sufficient to relieve pain (not associated with stent specifically) and alternative surgical treatment may be warranted. In these cases, patient data will be captured but non-device related cause captured as reason for subject stenting termination.]
- Assessment of retrograde urine reflux after placement of the ureteral stent, as determined by the visualization of urine in the distal ureter to the kidney using cystography after contrast gravity-filling of the bladder and assigning a urinary reflux grade based on:
  - Grade I: urine refluxes into the ureter only.
  - Grade II: urine refluxes into the ureter and up to the kidney without dilation.

- Grade III: urine refluxes into the ureter and kidney and causes mild dilation.
- Grade IV: urine refluxes into ureter and kidney and causes dilation without twisting of the ureter.
- Grade V: urine refluxes into ureter and kidney and causes significant dilation with twisting of the ureter.

- Visualization of distal coil in bladder, after stent placement. Document placement using a cystoscope.

2- Primary safety endpoint:  
Assessment of pain or irritative symptoms (incidence, severity) attributed to the ureteral stent as well as unplanned return visits to ED, OR, or clinic.

3- Secondary endpoint:

- USSQ Scale (Ureteral Stent Symptoms Questionnaire) [Time Frame: Day 3 as endpoint]
- Unplanned hospital visits or doctor visits related to the stent
- Medication use endpoint:
  - Physicians can prescribe standard medications such as alpha blocker (Tamsulosin), Anticholinergic (Oxybutynin), phenazopyridine (Pyridium), ibuprofen and Tylenol prn pain for the duration of the stent plus 1 day (post stent removal) (Document on CRF)
  - Requests for “breakthrough” pain medication (narcotics) would be at the request of the patient post procedure (not to be given as a standard dose). (Document on CRF)
  - Patients to keep medication diary in situations where patients are not taking medications as prescribed

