#### Screening/Enrollment:

- Patients will be screened for eligibility
- If eligible, patients will be enrolled in the study through signing of the Informed Consent Form
- Medical charts will be reviewed, demographics will be collected, and medications will be reviewed prior to surgery

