#### Day 0 (Stent Placement)

- Patients will be randomized to one of two study groups (Relief stent vs DJ stent)
- Medical charts will be reviewed and medications will be reviewed prior to surgery
- Stent will be placed per standard of care
- A intraoperative photo of the stent will be taken to confirm placement

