#### Post-stent Follow-Up:

- Post-operatively complete Ureteral Stent Satisfaction Questionnaire (USSQ) surveys at day 1, day 3, day of stent removal, and 2 days post stent removal (note day of removal) (between 7-10 days in normal practice (even up to 14 days):
- Medications will be tracked on the CRF at day 1, day 3, day of stent removal, and 2 days post stent removal
- Day 1 (12-30 hours after stenting procedure), subject will be evaluated by study personnel for acceptable procedural outcome.
- Document any unplanned hospital visits or doctor visits related to the stent  
Day 1, Day 3, Day of stent removal (i.e., Day 7-10), and 2 days post stent removal, subject will be evaluated by study personnel for ongoing tolerability and stent performance (e.g., drainage) in person or by phone.
- Direct or remote evaluation will be documented. If unusual levels of pain or other potentially serious complications are suspected, the subject will be brought in for Clinician evaluation.

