## 6.4 STUDY INTERVENTION COMPLIANCE

There will be three questionnaires completed by subjects at multiple different timepoints which will ensure study intervention compliance.

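### The stated objective includes a USSQ before stent placement, but the schedule and visit steps collect the USSQ only after surgery

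*Combined protocol and SAP*

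**What the plan says.** The synopsis (Section 1.1) and the secondary objectives in Section 3 give the same four time points: "Reporting the Ureteral Stent Symptoms Questionnaire (USSQ) before stent placement, after placement at day 3, prior to removal and post removal".

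In the Schedule of Activities (Section 1.3), the row "Ureteral Stent Symptoms Questionnaire" is blank at Screening/Enrollment and at Day 0. It is marked at Day 1, Day 3, stent removal (Day 7-10) and 2 days after removal (Day 9-12).

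Section 4.1, Post-stent Follow-Up, repeats this in prose: "Post-operatively complete Ureteral Stent Satisfaction Questionnaire (USSQ) surveys at day 1, day 3, day of stent removal, and 2 days post stent removal". The two pre-operative lists in Section 4.1 contain no questionnaire. Screening/Enrollment has eligibility, consent and "Medical charts will be reviewed, demographics will be collected, and medications will be reviewed prior to surgery". Day 0 has randomization, stent placement, an intraoperative photo and "Medical charts will be reviewed and medications will be reviewed prior to surgery".

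Section 3 fixes the USSQ secondary endpoint at Day 3. Sections 9.4.1 and 9.4.3 compare USSQ findings between arms with a Mann-Whitney U test or t-test (chi-square or Fisher's exact test for categorical items). Neither mentions a baseline score. Section 9.4.5 promises a baseline comparison of the two cohorts without naming variables.

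**The concern.** The objective and the schedule cannot both be followed as written. Staff normally work from the schedule, and Section 4.3 defines completion by the last visit or procedure in it. A patient could therefore count as complete without ever having given a pre-stent USSQ.

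The score cannot be obtained once the stent is in. It would also be the only patient-reported symptom score from before surgery, since the other pre-operative information is demographics, chart data and medications. Section 3 hypothesizes fewer irritative symptoms with the RELIEF stent, and patients enter with stones or strictures, so some may well have symptoms beforehand. Without a pre-stent score, nobody could see whether 25 patients per arm happened to start out different, or adjust for it.

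**Working it through.** **Step 1: time points side by side.**

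| USSQ time point | Objective (Sections 1.1, 3) | Schedule (Section 1.3) | Visit steps (Section 4.1) |
|---|---|---|---|
| Before placement | Yes | Blank at Screening and Day 0 | Not listed |
| Day 1 | No | Yes | Yes |
| Day 3 | Yes | Yes | Yes |
| Removal | Yes | Yes | Yes |
| After removal | Yes, no day given | Yes, 2 days after | Yes, 2 days after |

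Objective and schedule each have four time points and share three. There is one mismatch in each direction: pre-stent is stated but not scheduled, and Day 1 is scheduled but not stated.

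**Step 2: is the table reading safe?** The USSQ row has six cells for six visit columns, and the prose in Section 4.1 gives the same four post-operative times independently. The finding does not depend on the table layout. Section 4.1 expands the abbreviation with a slightly different name; I take it to be the same instrument because the abbreviation and the time points match the schedule.

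**Step 3: does another section supply the missing score?** Section 6.4 says "There will be three questionnaires completed by subjects at multiple different timepoints" but names neither instruments nor times. Section 8.1 mentions a questionnaire only alongside the Day 1 and Day 3 assessment of drainage. Section 9.4.5 would report a baseline score if one existed but does not schedule it. The Day 1 USSQ cannot stand in for a baseline, because it follows both randomization and stenting.

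**Step 4: size of the loss.** Target enrollment is 50 (25 per arm). With the schedule followed, 50 of 50 patients lack the pre-stent score.

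**Step 5: the plan's own power figure.** The only power statement (Section 9.2) is for reflux incidence: N = 50, w = 0.4, alpha 0.05. The noncentrality is 50 × 0.4² = 8, and the 1-df chi-square power is 80.7%, which agrees with the stated 80%. A pre-stent USSQ does not enter this calculation.

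**Step 6: what the score could add if used as a covariate.** The documents give no correlation r between the pre-stent and Day 3 scores, so r is assumed over a range. With 25 per arm and one covariate, the variance of the treatment difference is multiplied by (1 − r²)(1 + 1/46) = (1 − r²) × 47/46. The equivalent change in sample size is 46 / [47(1 − r²)] − 1:

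- r = 0.1: 46 / 46.53 − 1 = −1.1%
- r = 0.3: 46 / 42.77 − 1 = 7.6%, about 8%
- r = 0.5: 46 / 35.25 − 1 = 30.5%, about 30%

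Break-even is at r² = 1/47, so r = 0.146 (0.149 allowing for the lost degree of freedom). There is no gain below about 0.15.

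**The case against.** The strongest reply is that little is lost. The USSQ endpoint is Day 3, no planned analysis uses a pre-stent score, and randomization makes the unadjusted Day 3 comparison valid without one. This stands, and it limits the point to one descriptive element of one secondary objective.

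The loss is also conditional. The objective is itself protocol text, and a single site could collect the score on the strength of it. That is fair, but nothing in the schedule or visit steps would prompt anyone to do so.

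The sponsor might say that Day 1 was simply preferred to a baseline. If so, the synopsis and Section 3 need to say that; at present they say otherwise.

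Finally, the covariate figures in Step 6 rest on an assumed r and relate to a linear-model analysis. They do not carry over directly to the Mann-Whitney test that the plan also allows. The finding does not depend on them.

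A reader might infer that without a baseline the Day 3 comparison is biased, or that the trial loses power. The documents support neither. Allocation is randomized 1:1, the planned test is between arms at Day 3, and the power statement concerns reflux.

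**Conclusion.** The inconsistency is real and should be corrected, at moderate weight. Three of the four USSQ time points in the objective are scheduled. The fourth would be missing for all 50 planned patients, irrecoverably, provided that the schedule is what staff follow. The consequence is that the pre-stent part of a stated secondary objective could not be reported, and symptom imbalance before stenting could be neither seen nor adjusted for. The Day 3 USSQ comparison and the primary reflux endpoint stand as planned. Leaving the baseline out of the Day 3 test is not an error; adjusting for it would be an optional gain whose size depends on an r that the documents do not give.

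**What to change.** 1. Add a USSQ mark to the Schedule of Activities at Day 0 and a matching line in the Day 0 steps of Section 4.1, to be completed before randomization and surgery. The order matters because the trial is open label and randomization is the first item in the Day 0 list. Screening/Enrollment would also satisfy the objective and precedes randomization, but the score could then be up to 90 days old.
2. State in Section 9.4.5 that the pre-stent USSQ is reported by arm.
3. Reconcile Day 1: add it to the objective in Sections 1.1 and 3, or state that it is collected but is not part of the objective. Without this step the sections still disagree.
4. If no baseline is wanted, remove the pre-placement time point from Sections 1.1 and 3 and make the same Day 1 correction.

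The cost is one more questionnaire at an existing contact, a few minutes per patient and a handful of text edits.

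Optional, and not the correction of an error: in Sections 9.4.1 and 9.4.3, analyse the Day 3 USSQ by ANCOVA with the pre-stent score as covariate. It brings no precision gain if r is below about 0.15.
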